2.2 Secondary Objectives

2.2.1 To evaluate complete remission (CR) rates, duration of remission, and toxicity/treatment-related mortality of clofarabine in comparison with standard therapy (daunorubicin & cytarabine) in newly-diagnosed AML patients age \geq 60 years.

2.2.2 To evaluate the feasibility of consolidation with reduced-intensity conditioning and allogeneic hematopoietic stem cell transplantation from HLA-identical donors in patients who achieve a response to induction therapy, including the incidence of successful engraftment, acute and chronic graft-versus-host disease, transplant-related mortality, and its impact on overall survival in comparison to patients receiving chemotherapy.

2.2.3 To evaluate the duration of remission and disease-free survival of patients in complete remission following completion of consolidation therapy who are subsequently randomized to receive scheduled low-dose decitabine maintenance in comparison with observation.

2.2.4 To perform expression and methylation profiling on all patients receiving decitabine and to correlate their integrated epigenetic signatures with response to decitabine.

2.2.5 To examine the epigenetic profiles of remission marrow in patients randomized to observation vs. decitabine to determine whether epigenetic signature of apparently morphologically normal bone marrow is predictive of relapse or response to decitabine maintenance.

2.2.6 To explore the possible association of response to clofarabine with ABC-transporter P-glycoprotein (Pgp).

2.2.7 To assess the intensity of expression of CXCR4 on diagnostic leukemia cells and to correlate this parameter with other established prognostic factors

2.2.8 To assess the entire spectrum of somatic mutations and affected pathways at diagnosis of AML and elucidate the association between gene mutation and outcome.

2.2.9 To examine the impact of smoking, obesity, regular acetaminophen use, regular aspirin use, benzene exposure, living in a rural/farm environment and some other underlying exposures and lifestyle factors associated with AML development on OS.

Rev. 2/13

Rev. 2/12

Rev. 2/12

Rev. 2/13

Rev. 2/13

2.2.10 To investigate potential correlative results between array CGH findings and acute myeloid leukemia patient characteristics.

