Another goal of the correlative studies is to explore the possible association of response to clofarabine with ABC-transporter P-glycoprotein (Pgp). We hypothesize that the relative expression of Pgp will determine differential activity of clofarabine in subsets of patients who overexpress Pgp, and will manifest itself in the CR rate. An aliquot of bone marrow or peripheral blood from pre-treatment samples will be evaluated for Pgp protein expression by flow cytometric assessment of binding of anti-Pgp antibody, MRK-16. In E3999, MRK-16 binding significantly correlated with P-glycoprotein function as a drug-efflux pump. We assume that 360 patients will receive clofarabine and 87% of those patients will submit samples and will have sufficient material for analysis. We assume about 20% of patients will overexpress Pgp and the CR rate of the patients who

overexpress Pgp is 30%. With 63 patients who overexpress Pgp the study will have 80% power to detect an effect size of 0.80 at the two-sided significance level of 0.05 using a Wilcoxon rank sum test. Effect size is defined as the difference of the expression of Pgp between CR patients and non-CR patients divided by the common standard deviation of the two groups. Table 4 presents the effect size to be detected with 80% power under various percentages of patients overexpress Pgp and various CR rates of those patients.

Table 4: Effect Size of the Expression of Pgp between CR Patients and non-CR Patients (two-sided $\alpha = 0.05$, power=80%)

CR rate of the patients who overexpress transporter	Percentages of patients overexpress transporter	Effect size to be detected
30%	40%	0.56
	30%	0.65
	20%	0.80
35%	40%	0.54
	30%	0.62
	20%	0.76

Rev. 2/12

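### The Pgp analysis is confined to over-expressors (about 63 of 313 measured clofarabine patients), which makes it a poor test of whether Pgp is associated with response to clofarabine

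*Combined protocol and SAP*

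**What the plan says.** Secondary objective 2.2.6 is: "To explore the possible association of response to clofarabine with ABC-transporter P-glycoprotein (Pgp". Section 1.6.1 states a wider purpose, which is to establish how Pgp expression affects the CR rate and overall survival.

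Section 9.8 gives the analysis. Its hypothesis begins: "We hypothesize that the relative expression of Pgp will determine differential activity of clofarabine", and it places this in subsets that over-express Pgp and expects it to show in the CR rate. The sample assumption is: "We assume that 360 patients will receive clofarabine and 87% of those patients will submit samples and will have sufficient material for analysis". It continues: "We assume about 20% of patients will overexpress Pgp", with a 30% CR rate in that group. The power statement follows: "With 63 patients who overexpress Pgp the study will have 80% power", for an effect size of 0.80. The contrast is then fixed: "Effect size is defined as the difference of the expression of Pgp between CR patients and non-CR patients", in units of the common SD. Table 4 repeats the calculation for over-expression of 20%, 30% and 40% and for CR rates of 30% and 35%.

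For Pgp, section 9.8 describes no analysis of patients below the over-expression threshold, no standard-arm comparison, no treatment-by-Pgp term and no survival analysis. The same section plans treatment-by-mutation interaction tests for the somatic mutations. For CXCR4 it uses every patient with material, 315 per arm.

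**The concern.** If Pgp matters for response to clofarabine, most of the information lies in the contrast between low and high expressors. Selecting on high Pgp removes that contrast and leaves only the gradient within the upper tail, in about a fifth of the measured patients. A null result there would say little about objective 2.2.6.

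The rationale in sections 1.6.1 and 10.5 is that clofarabine is not a Pgp substrate, so a flat relation within over-expressors is a plausible outcome. A small, range-restricted comparison could not separate that from an association it had no means of seeing.

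The size of the subset is also open. No cut-off for over-expression is given. Section 1 says Pgp is expressed in roughly 70% of older patients, while section 9.8 assumes 20% over-express. These may be different definitions, but the plan does not say.

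**Working it through.** **Inputs.** From section 9.8: 360 clofarabine patients; 87% with usable material; 20%, 30% or 40% over-expressing; CR 30% or 35% among over-expressors; two-sided alpha 0.05; 80% power; Wilcoxon rank sum test. The 40% overall CR rate used below is one of the two rates in the CXCR4 paragraph of section 9.8. Applying it to clofarabine patients in the Pgp analysis is an assumption.

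**Step 1: who is in the stated calculation.** Measured: 360 × 0.87 = 313. Over-expressors: 313 × 0.20 = 63; at 30%, 94; at 40%, 125. At 20%, 313 − 63 = 250 measured patients are left out.

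**Step 2: reproduce the plan's figure.** The claim is "80% power to detect an effect size of 0.80 at the two-sided significance level of 0.05 using a Wilcoxon rank sum test". With 30% CR the groups are about 19 and 44. The normal approximation is

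d = (1.96 + 0.84) × √(1/n1 + 1/n2) × √(π/3),

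which gives 0.79. The noncentral t version, with the same Wilcoxon efficiency of 3/π, gives 0.804. Simulated power of the Wilcoxon test at 0.80 SD is 79.5%. All of Table 4 reproduces:

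| CR rate | Over-expressing | N | Stated | Recomputed |
|---|---|---|---|---|
| 30% | 40% | 125 | 0.56 | 0.564 |
| 30% | 30% | 94 | 0.65 | 0.653 |
| 30% | 20% | 63 | 0.80 | 0.804 |
| 35% | 40% | 125 | 0.54 | 0.541 |
| 35% | 30% | 94 | 0.62 | 0.627 |
| 35% | 20% | 63 | 0.76 | 0.772 |

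The match confirms that N is the over-expressors alone.

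**Step 3: the same formula on all 313.** With 40% CR (125 against 188) the detectable effect is 0.33 SD, and 0.33–0.35 SD for CR rates of 30–45%. This is in the SD of the whole sample, whereas 0.80 is in the SD of the subset, so the two cannot be compared directly.

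**Step 4: put both on one scale.** Assume Pgp is standard normal, the log-odds of CR are linear in Pgp, overall CR is 40%, and over-expressors are the top 20%. The SD of Pgp within the top 20% is then 0.468. Under this model the CR versus non-CR difference, in SD units, is approximately slope × SD of the group analysed:

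- slope 0.30: 0.30 SD in all patients; 0.30 × 0.468 = 0.14 SD in the subset;
- slope 0.35: 0.35 SD in all patients; 0.35 × 0.468 = 0.16 SD in the subset.

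CR in the top fifth is then about 30% and 29% respectively, in line with the 30% assumed in section 9.8. Simulating the Wilcoxon test over these slopes gives power of about 71–83% with all 313 patients and about 6–8% with the 63, barely above the 5% test level.

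**Step 5: a treatment-by-Pgp term.** Take 63 high and 250 low expressors per arm and a Wald test on the log-odds scale. All CR rates are assumed except the 30% for clofarabine-treated over-expressors, which is section 9.8's figure; 42.5% in the low expressors keeps clofarabine at 40% overall.

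| Standard, high / low | Clofarabine, high / low | Power |
|---|---|---|
| 20% / 45% | 40% / 40% | 76% |
| 25% / 44% | 40% / 40% | 51% |
| 30% / 43% | 40% / 40% | 27% |
| 20% / 45% | 30% / 42.5% | 29% |
| 25% / 44% | 30% / 42.5% | 11% |

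**The case against.** The plan's arithmetic is right and openly stated, so a reader who concludes that the power claim is wrong goes too far. Power is low only for smaller within-subset effects, for example 43% at 0.50 SD and 22% at 0.33 SD. Table 4 also covers larger subsets. This stands. What it does not answer is that a 0.80 SD difference inside a truncated range corresponds to a far stronger association than a difference of that size across all patients.

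A reader might also infer that the plan cannot test differential activity at all without a control arm. The documents do not support that. Objective 2.2.6 is exploratory and names no comparator, and the hypothesis in section 9.8 can be read as a gradient within over-expressors, which is what the plan powers. The case for the standard arm rests on the rationale in sections 1.6.1 and 10.5, not on the objective. Nor would adding that arm settle the matter: with Pgp split at 20%, the interaction test may itself have as little as 11% power.

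Two further points stand. Sample submission is mandatory, but sections 7.3 and 10.1.1 make correlative use subject to consent. And section 9.8 does not say that other patients will be excluded from every Pgp analysis; it simply describes no other one.

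**Conclusion.** The point holds as a mismatch between objective and analysis. The stated 80% power at 0.80 SD is correct, but the over-expressor comparison is an inefficient test of objective 2.2.6 and leaves the CR and survival aim of section 1.6.1 without a matching analysis.

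Under the model in the working, using all measured patients raises power from about 6–8% to about 71–83%. Those figures depend on normally distributed Pgp, a log-linear effect across its whole range, 40% overall CR and a top-20% cut. If Pgp acted only above a threshold within the upper tail, the advantage would be smaller.

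The tempting summary that the detectable effect falls from 0.80 to 0.33 SD should not be used, because the units differ. Severity is minor: this is one exploratory correlative objective, and no primary conclusion depends on it.

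**What to change.** In section 9.8, make the main Pgp analysis the association of Pgp, as a continuous variable, with CR in all clofarabine patients with a usable measurement. Keep the over-expressor comparison and Table 4 as secondary, and state the cut-off that defines over-expression. Say whether the survival aim in section 1.6.1 is to be analysed.

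As an exploratory addition, fit a logistic model for CR over both arms with a treatment-by-continuous-Pgp term, in line with the interaction tests already planned for mutations, among patients whose samples may be used for correlative work. State that its power is limited: for Pgp split at 20%, about 11–76% depending on the assumed CR rates.

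The cost for the main analysis is SAP wording, with no new samples from clofarabine patients. The two-arm model uses standard-arm specimens that are already collected, subject to consent. This is a free improvement.

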9.9 Accrual

If the interim analysis of the maintenance comparison (described in Section [9.5](#)) demonstrate the study should reopen, we will reopen the study to accrue an additional 52 patients to the second randomization, to finish the accrual goal of 172 patients. This requires about 74 CR/CRI patients to be pre-registered after their induction therapy. Based on the accrual rate of the first 120 randomized patients, we anticipate the additional accrual could be completed with 1.8 years.

9.10 Anticipated Accrual by Gender and Ethnicity

Based on previous data from E3999, the anticipated accrual in subgroups defined by gender and race is:

Ethnic Category	Sex/Gender		Total
	Females	Males	
Hispanic or Latino	11	7	18
Not Hispanic or Latino	335	448	783
Ethnic Category: Total of all subjects	346	455	801
Racial Category			
American Indian or Alaskan Native	0	0	0
Asian	2	2	4
Black or African American	17	18	35
Native Hawaiian or other Pacific Islander	0	0	0
White	327	435	762
Racial Category: Total of all subjects	346	455	801

9.11 Study Monitoring

This study will be monitored by the ECOG-ACRIN Data Monitoring Committee (DMC). The DMC meets twice each year. For each meeting, all monitored studies are reviewed for safety and progress toward completion. When appropriate, the DMC will also review interim analyses of outcome data. Copies of the toxicity reports prepared for the DMC meetings are included in the study reports prepared for the ECOG-ACRIN group meeting (except that for double blind studies, the DMC may review unblinded toxicity data, while only pooled or blinded data will be made public). These group meeting reports are made available to the local investigators, who may provide them to their IRBs. Only the study statistician and the DMC members will have access to interim analyses of outcome data. Prior to completion of this study, any use of outcome data will require approval of the DMC. Any DMC recommendations for changes to this study will be circulated to the local investigators in the form of addenda to this protocol document. A complete copy of the ECOG-ACRIN DMC Policy can be obtained from the ECOG-ACRIN Operations Office - Boston.

Rev. 2/12,
2/13, 7/14

10. Correlative Studies

NOTE: ECOG-ACRIN requires that all biological samples submitted be entered and tracked via the online ECOG-ACRIN Sample Tracking System. An STS shipping manifest form must be generated and shipped with the sample submissions. See Section [10.8](#).

10.1 Immunophenotype and Molecular Genetics

Immunophenotyping has become an essential part of the diagnostic work-up of all leukemia patients. In fact, the diagnosis of leukemia without immunophenotypic characterization is no longer acceptable. ECOG-ACRIN has, therefore, developed a model system for antigenic data collection that requests specimens from all patients entered on ECOG-ACRIN leukemia treatment trials be studied by ECOG-ACRIN's Leukemia Translational Studies Laboratory (LTS). In addition to establishing the leukemia subtype, this centralized testing and data collection has allowed that research questions of clinical relevance be applied to a growing database (e.g., definition of prognostically significant antigen expression levels to eventually yield specific treatment subcategories).

Depending on the study protocol and tissue availability, anti-coagulated (heparin, EDTA, ACD) peripheral blood or bone marrow or both are to be submitted to the LTS. The dual function of the LTS in eligibility determination and sample processing/banking (ECOG-ACRIN's Leukemia Tissue Bank), facilitates the distribution of fresh or adequately processed specimens to other laboratories involved in protocol-embedded correlative studies, such as the analyses of epigenetic and genetic lesions.

In addition to the study of abnormal hematopoietic cells, the focus of research on circulating serum factors in patients with leukemia or myelodysplasia has increased. Two tubes of coagulated peripheral blood (red top tubes) are requested for future research studies that may aim at identifying pathogenetic, diagnostic, or prognostic factors associated with leukemia or myelodysplasia.

Serum and cells from peripheral blood or bone marrow from patients entered on studies of hematologic malignancies are stored in ECOG-ACRIN's Leukemia Tissue Bank for future laboratory studies. The bank provides the scientific community a source of leukemia specimens that are collected, processed, and maintained following quality control and quality assurance guidelines. The bank will accommodate requests from investigators within and outside ECOG-ACRIN in a timely and efficient manner, with respect to tissue type, tissue preparation, and most importantly, biologic characteristics of specimens.

10.1.1 Sample Collection and Submission Schedule

Bone marrow, peripheral blood, and smears **must** be submitted at the following time points (**Mandatory Submissions**):

- Pre-Registration
- Notification to the submitting institution:
The ECOG-ACRIN Leukemia Translational Studies Laboratory will notify the submitting institution of the results of the centralized immunophenotyping within 4-6 hours of receipt of the samples.

Rev. 2/12

Rev. 12/13

- Time of Outcome Following Induction – Prior to Consolidation (at time of response assessment or off-study, whichever occurs first)
- End of Consolidation (Prior to 2nd Randomization - Step 3)
- Relapse

Rev. 12/13

Bone marrow and peripheral blood will also be used for the optional correlative studies per patient consent.

Peripheral blood and buccal rinse [preferred] or swabs (baseline only) are to be submitted at the above time points for banking per patient consent.

Rev. 2/12

Samples are to be shipped on the day they are drawn. If this is not possible, call the LTS.

If you have questions, contact the LTS at [contact].

10.1.2 Sample Preparation Guidelines

NOTE: All cooperative groups should send specimens to the ECOG-ACRIN Leukemia Translational Studies Laboratory.

[name] institutional regulations require that she receive a copy of the patient's consent and a copy of the HIPAA authorization at time of or prior to submission of the pre-study samples.

All samples must be clearly labeled with the ECOG-ACRIN protocol number (E2906), ECOG-ACRIN patient sequence number, patient's initials, date of collection, and sample type.

10.1.2.1 The following are to be submitted:

1. **MANDATORY AT ALL TIME POINTS:** Heparinized bone marrow aspirate. The laboratory will accept any amount as long as it represents a first pull. It is imperative that aspirate from a separate first pull be submitted. **DO NOT SUBMIT THE SECOND OR THIRD PULL OF ASPIRATE FROM THE SAME ASPIRATION SITE.** With every pull from the same aspiration site, the blast count decreases due to hemodilution. Ideally, 2-3 mL of aspirate from a separate aspiration site should be submitted

For patients with an inaspirable bone marrow ("dry tap"), or if a bone marrow has been done previously and the patient refuses to have another aspiration done, call [name] laboratory at [contact] to discuss the case and the possibility for submitting peripheral blood only. Be prepared to report the WBC count and the blast count in the peripheral blood at the time of the call.

2. **MANDATORY AT ALL TIME POINTS:** Heparinized or EDTA peripheral blood (four (4) green or purple top tubes, 30-40 mL).

Rev. 12/13

Rev. 2/12, 12/13

3. MANDATORY AT ALL TIME POINTS: At least two (2) Wright-Giemsa stained bone marrow smears and one (1) Wright-Giemsa stained peripheral blood smear.

NOTE: These smears will be forwarded to [name] at Stanford University for morphologic review, if necessary.

Rev. 2/12

4. MANDATORY AT ALL TIME POINTS: A copy of the institutional pathology report on the bone marrow must be submitted. If the pathology report is not available at the time the samples are mailed to the ECOG-ACRIN Leukemia Translational Studies Laboratory, the report must be FAXED at a later time to: [contact]. The pathology report must include cytogenetic results and any results from fluorescence-in-situ (FISH) hybridization and/or molecular studies done at the submitting institution.

Rev. 12/13

5. Two (2) red top serum tubes of peripheral blood (15-20mLno anticoagulent)

Rev. 12/13

- Submit from patients who answer "YES" to "*I agree to provide additional specimens for research.*"

NOTE: If samples designated for banking only are not submitted, please note the reason in the comments section of the Sample Tracking System.

Rev. 2/12

6. Buccal Cell Samples

Most commonly, institutions will have buccal swab kits for the collection of cells for HLA-typing. Alternatively, Scope, a commercial brand mouthwash, or normal saline in a small sealed bottle can be given to the patient for a mouthwash.

Aseptic techniques must be used to collect buccal cells from patients on-site and buccal cells must not be contaminated with cells from any other source. Patients should not brush their teeth or consume food prior to buccal cell collection.

If a cytobrush is used, the collection end should not be touched and the patient should not scrape his/her cheek too vigorously. The inside of the cheek should be scraped 6 times. Several models of cytobrushes are available, such as the Omni swab or Bio-Swab from Arrowhead Forensics or the Cyto-Pak CytoSoft Brush from Medical Packaging Corp.

- If mouthwash (e.g. Scope) or normal saline is used, the patient should pour approximately 10cc of mouthwash or saline into his/her mouth and

Rev. 12/13

vigorously swish it against the cheeks for 10 seconds and deliver the solution into a labeled 15cc polypropylene test tube or a sterile urine cup. Among mouthwashes, the Scope brand fares best in collecting buccal cells for the preparation of high-quality DNA in high yield.

Rev. 12/13

- It is important that buccal cells do not dry out during shipping. Institutions are advised to seal the container containing the buccal cells tightly. Ship containers on ice-packs, together with the patient's peripheral blood and bone marrow specimens.
- Submit from patients who answer "YES" to "*I agree to provide additional specimens for research.*"

NOTE: Buccal rinse (preferred) or swabs are strongly encouraged to be collected at baseline, but can be collected at any other time during the study if necessary.

10.1.3 Shipping Procedures

Log the shipment into the ECOG-ACRIN STS the day of shipment. If the STS is unavailable, an Generic Specimen Submission Form (#2981) must be submitted with the samples. Once STS is available, retroactively log the shipment into STS, using the actual collection and shipping dates.

Rev. 12/13

The LTSI must be notified by telephone the day of shipment.

Fax or Email to [name] is NOT Acceptable.

[contact]

Rev. 12/13

During off hours, all information regarding the shipment should be left on the answering machine in the LTSI including:

E2906 Sequence Number

Patient's Initials

Type of Specimen Shipped

Name, Telephone Number, and Institution

Follow the directions given in the phone message.

For questions regarding the shipment, [name] and her staff can be reached at the cell phone numbers provided on the recorded message. Please always try [name] first. Questions can also be addressed to [name] via e-mail ([contact]), however, please do not use e-mail for shipment notifications.

Rev. 12/13

Rev. 2/12

Rev. 2/13

Heparinized bone marrow and peripheral blood samples or EDTA peripheral blood samples, coagulated blood in red top tubes and buccal cells must be sent fresh (on the day of collection) on **cool**

packs (do not freeze and do not use ice cubes) by overnight courier (preferably Federal Express) to arrive within 24 hours to:

Rev. 12/13

[name].
Montefiore Medical Center-North Division (Wakefield)
[name]
[name]
[name]
[contact]
[contact]

An STS shipping manifest form must be generated and shipped with all sample submissions.

Rev. 12/13

Please enter all information into the STS, including time and date of specimen collection and peripheral blood WBC count and blast count.

The LTSI is open to receive shipments Monday through Saturday. Shipments on Fridays for Saturday delivery must have "Saturday Delivery" marked on the overnight courier slip.

If samples need to be drawn late at night, on Sunday, or on a holiday when Federal Express does not operate, keep the samples in a refrigerator between 10 and 15 degrees Celsius until the next day when it can be shipped.

Rev. 12/13

In general, always ship specimens the day before a holiday for delivery the day after the holiday.

